program information on the Project website and can choose to complete the registration/screening form on the registration website. Only eligible participants who have provided informed consent will be provided access to the full modules (password protected), links to the Qualtrics surveys, and links to the HIPAA compliant Zoom meeting invites. All survey data will be collected via Qualtrics and will be stored on the UNC Charlotte servers and systems. Additionally, all recordings of the sessions and focus groups will be stored on the UNCC servers and systems. All assessment data and recordings will only be able to be accessed by members of the research team.

"Cuidando Juntos" is the name of the Spanish intervention for Latino dementia caregivers.

The CAB members are only reviewing and providing feedback on program materials, assessments, and documents. They are not functioning as participants, and will not have access to any participant data.

The links were met to direct IRB members to the Caregiver TLC Website in English as the Caregiver TLC program is the program on which the Spanish version will be based. The links have been removed. The Caregiver TLC program was evaluated in a previous study already approved by the UNC Charlotte IRB.

The content of the surveys has not been yet fully developed. The first goal of this study is to develop a program and assessment that are culturally adapted for Latino dementia caregivers. The development of such materials is expected to take about six months. Once the materials are developed they will be added to the IRB for approval. Participants will not be contacted until materials are developed.

Members in the focus groups will be asked to submit written feedback and complete semi-structured focus group sessions, thus semi-structured interviews will be the means of data collection for the focus groups. The semi-structure questions has not yet been fully developed. The development of such materials is expected to take about six months. Once the materials are developed they will be added to the IRB for approval.

Participants will not be contacted until materials are developed.

*** 4. Duration of participation: Describe the 1) Total time commitment for the participant and 2) time commitment for each activity or component if applicable. E.g., duration for each survey, interview, follow-up, debriefing, etc.**

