We will assess caregivers approximately one week prior to the training one week after completing the program. These measures are standard in the caregiving literature, and focus on both the positive and potential negative aspects of caregiving. At each occasion, they would require approximately an hour to complete. In addition to these assessments, caregivers will attend 6 weekly sessions to complete the program. Participants will also answer semi-structure interview questions as part of focus group discussions after completing the six week sessions.

The estimated duration of participation is approximately 2 months.

After qualifying participants are consented they will be assigned to participate in the "Cuidando Juntos" program group. Once assigned, participants will complete a pre assessment survey approximately one week before beginning the program. The pre-assessment survey will be completed virtually using Qualtrics and will take approximately 40 minutes to complete. Participants will then complete the six weekly "Cuidando Juntos" program sessions, each lasting two hours. One week after completion of the sessions participants will complete a post assessment survey virtually using Qualtrics, which will take approximately 40 minutes to complete. Between one and two weeks after completing the program sessions, all participants in the program group will be invited to participate in a virtual focus group via HIPAA zoom platform. Participants will be ask to respond to semi-structured questions about the program during the focus group. The group will be lead by a bilingual/bicultural member of the research team. The focus group will last two hours. Total participation for the duration of the study will be approximately ten week for participants.

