materials; each initial meeting will focus on one workshop session and feedback will be obtained on: how content is presented; appropriateness of examples and action plans; how to increase social connectedness -particularly with family members – within the context of that workshop's focus. The CAB will also review the program Website that is in English, and make recommendations to make it user-friendly for Latino caregivers. The CAB will recommend ways to use this website to increase social connectedness. CAB members need to identify as Latino, be bilingual, and have the necessary time and skills to participate. To meet Aim 2 (Stage 1B trial), based on this feedback, a preliminary adapted version will be tested in an Stage 1B trial (pre- post design). We will recruit 20 Latino caregivers and all will receive the intervention (with n=10 in each group, run sequentially). We will make refinements (if needed) based on participant and CAB feedback between the first and second group. We will collect qualitative and quantitative data with several metrics (described below). Caregivers need to be men and women, 45 years and older, who identify as primary caregivers of a PLWD with whom they co-reside or live close by. A stress rating will be used so that at least a moderate level of stress related to caregiving is endorsed. Willingness to complete interviews and surveys and provide feedback are also necessary. To address Aim 3, (mechanisms) we will assess changes in loneliness and social support and anticipate that Latino caregivers who demonstrate decreases in loneliness and increases in social support will experience lower stress levels, burden and depression.

6. Analytic Plans: We will collect qualitative and descriptive quantitative data using mixed methods: 1. Individual semi-structured interviews with members of the CAB to ask them about caregivers' needs, supportive services, cultural views and normative expectations about care. 2. Data from Focus Group participants on feasibility and acceptability of the adaptation and refinement. 3. Descriptive pre-post data from the early developmental trial (20 caregivers). Data Analytics.

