a. Metrics to assess acceptability of the adapted Caregiver TLC program at conclusion of the early stage trials studies: - Number of “hits” to website and program materials; - % completed action plans; - 6 point self-report Likert scales for: program satisfaction; new skills learned; usefulness of skills; helpfulness of skills; likelihood of using skills in future. b. To measure the mechanism of social connectedness, we will administer the following before & after intervention. - Lubben Social Network Scale-6, Spanish translation (culturally adapted as well as translated into Spanish; Vilar-Compte, Vargas-Bustamante & Lubben, 2018). It is a measure of social isolation (by identifying and counting people in the network including family/ friends and identifying who to talk with about private matters”); -To measure Loneliness we will use the UCLA Loneliness Scale (full version, 20 items). Feelings of loneliness maybe inversely related to feeling connected and supported by family and friends (Russell, Peplau & Cutrona, 1980). c) Clinical outcomes: to be collected before & after early intervention trials: - Perceived Stress Scale, 10 item version (Cohen et al., 1983), available in Spanish; - Zarit Caregiver Burden 6-item version (Higginson, et al, 2010), translated into Spanish (Martin-Carrasco et al., 2010), and PHQ-9 to assess depressive symptoms (Kroenke & Spitzer, 2002; available in Spanish). d) We also assess for the role of Familism and Acculturation using the scales developed by Marin, Sabogal et al. (1987). Highly acculturated Latino dementia caregivers are likely to more extensively use support services outside the home (and rely less on family) to care for PLWD.

7. Future Directions/ Next Steps: This work is regarded as preliminary to development of an Stage II efficacy trial grant proposal to submit in 2024 which will test the acceptability of the culturally adapted Caregiver TLC in a rigorous controlled trial. We aim to develop an RO1 level multi-site Stage III-IV trial to test the efficacy of this virtual adapted Caregiver TLC program with Latino caregivers in different parts of the US.

Background Questions:

Please answer the questions below in regard to your project. Not to exceed 1 page.

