- C) What are the main sources of informal and formal support available for Latino caregivers providing care to PLVD in the community? **SPANISH:** Indicar los servicios de apoyo informal y formal disponibles para Latinos que cuidan de familiares con demencia en la comunidad.
- D) What are the main cultural barriers/opportunities for Latino caregivers providing care to PLVD in the community? **SPANISH:** Indicar los aspectos culturales que son barreras o facilitadores para Latinos que cuidan a familiares con demencia en la comunidad.

- 2. Focus Group to included program facilitators and consented participants in the pilot demonstration to report on the feasibility and acceptability of the adaptation:**

Sample questions (English/Spanish):

- A) What are the main difficulties Latino caregivers may encounter with the Caring Together educational program regarding content topics, activities, structure, design, resources, and use of technology? **SPANISH:** Indicar las dificultades con diversos aspectos del programa para Latinos que cuidan de familiares con demencia (sobre el contenido, actividades, estructura, diseño, recursos y uso de la tecnología)?
- B) What are the expected levels of satisfaction and acceptability of the Caring Together educational program among Latino caregivers of PLVD in the community? **SPANISH:** Indicar las expectativas de aceptación y satisfacción con el programa para Latinos que cuidan de familiares con demencia en la comunidad.
- C) What are the main values recognized/ignored by the Caring Together educational program for Latino caregivers of PLVD in the community? **SPANISH:** Indicar los valores culturales adoptados/ignorados por el programa para Latinos que cuidan de familiares con demencia.

3. Descriptive pre-post data from the early developmental trial (20 caregivers). Measures to assess the feasibility and acceptability of the program by participants in the pilot study.

Sample questions (English/Spanish):

- A) Percentage of Completed action plans. **SPANISH:** Indicar porcentaje de Latinos que completan el plan de acción del programa.
- B) Likert six-point self-report scales for: program satisfaction; new skills learned; usefulness of skills; helpfulness of skills; likelihood of using skills in future. **SPANISH:** Uso de escalas de tipo Likert para medir los niveles de satisfacción sobre el programa, el uso y utilidad de las habilidades y destrezas aprendidas, las estrategias y uso anticipado de las mismas.

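### Appendix 3 puts facilitators and caregivers in one acceptability focus group, the procedures describe a participant group, and nothing keeps the two apart

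*Combined protocol and SAP*

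**What the plan says.** Appendix 3 (the measures attachment) lists three data sources. Item 1 covers the Community Advisory Board (CAB). Item 2 is headed "Focus Group to included program facilitators and consented participants in the pilot demonstration to report on the feasibility and acceptability of the adaptation", and its sample questions ask about difficulties with the program, expected satisfaction and acceptability, and values the program recognises or ignores. Item 3 covers pre-post data and "Measures to assess the feasibility and acceptability of the program by participants in the pilot study".

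The IRB application, Methods and Procedures, question 4 (duration of participation), describes the session differently. Between one and two weeks after the last program session, "all participants in the program group will be invited to participate in a virtual focus group via HIPAA zoom platform" for two hours, and "The group will be lead by a bilingual/bicultural member of the research team". Facilitators are not mentioned. Question 3 describes participants consenting before they receive the Zoom link and adds that "Members in the focus groups will be asked to submit written feedback and complete semi-structured focus group sessions". The grant application's analytic plan refers to "Data from Focus Group participants on feasibility and acceptability of the adaptation and refinement". Question 6 (data analysis) says only that focus-group data will undergo content analysis.

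**The concern.** Item 2 of Appendix 3 names one group with two constituencies. The caregivers have just spent six weekly two-hour sessions with the facilitators. In Session 6 (Appendix 2) the facilitators hand out certificates and say something positive about each caregiver. One to two weeks later the caregivers are asked what was difficult and which values were missed. With those facilitators in the meeting, some caregivers may hold back.

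Feasibility and acceptability are among the questions this Stage I pilot is best placed to answer. It states no quantitative hypothesis, and its data analysis plan acknowledges a small sample and limited power. The grant application also says that the program may be refined between the first and second group on the basis of participant and CAB feedback. Criticism that is not voiced in the focus group is lost to that step unless another source picks it up. A content analysis that pools facilitator and caregiver statements would also make it hard to tell whose view is being reported.

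**Working it through.** No arithmetic applies. The documents attach no sample size, error rate or effect size to the focus group, so the check is a comparison of the relevant sections.

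**Who attends.**
- Appendix 3, item 2: program facilitators and consented participants, under a single item with a single question set.
- Methods and Procedures, question 3: participants. Facilitators are not mentioned in connection with the focus group.
- Methods and Procedures, question 4: participants in the program group. Facilitators not mentioned.
- Grant application, study design and analytic plan: focus-group participants. Facilitators not mentioned.

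The plain reading of the first entry is a mixed group, and the other three describe a participant group. None says that facilitators are absent, and none says that the two constituencies meet separately.

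**Who moderates.** Question 4 names a member of the research team. It does not say that this person did not deliver the sessions. The project website description lists facilitators and project team members as separate users, which suggests different people but does not rule out overlap.

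**How the data are analysed.** Question 6 gives content analysis with no step that separates facilitator from caregiver statements.

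**What other acceptability evidence exists.**
- The grant application has a list headed "Metrics to assess acceptability of the adapted Caregiver TLC program at conclusion of the early stage trials studies". It contains website hits, percentage of completed action plans, and "6 point self-report Likert scales for: program satisfaction; new skills learned; usefulness of skills; helpfulness of skills; likelihood of using skills in future". The focus group is not in that list.
- Appendix 3, item 3, repeats the action-plan and Likert measures.
- Focus-group members also give written feedback. The documents do not say what it asks or whether facilitators see it.
- Session 6 ends with an overall evaluation poll, held during the facilitators' own session.
- Session and focus-group recordings are reviewed for delivery and acceptability issues (Identifier Details, question 2).

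The focus group is therefore one source among several. The others do not fully replace it. Usage counts and satisfaction ratings do not show what failed, and action plans are developed in Session 6 with prompts and help from facilitators. Among the participant sources whose content is described, only the focus group has stated questions on difficulties and on values the program ignored.

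**The case against.** The strongest reply is that joint attendance is not established. Item 2 is one ungrammatical line in a list of data sources and may only record who supplies focus-group data. The procedural sections are more specific, and they describe a participant group under a research team member. This stands in part. A reader might infer from Appendix 3 that mixed sessions are the settled design, and the documents do not support that. They show two descriptions that differ and no rule that decides between them.

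Second, a reader might infer that the pilot's main acceptability evidence is compromised. That does not stand. No section ranks the focus group first, the grant's own list of acceptability metrics omits it, and there is also written feedback, a poll and a review of recordings. Nor does the focus group alone drive refinement. The grant application names participant and CAB feedback in general, and the CAB reviews materials by a separate route.

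Third, the sample questions are phrased about caregivers in general, invite criticism, and do not ask about facilitator performance. Certificates are awarded before the focus group, so facilitators hold no later benefit that the documents show. Both points weaken the mechanism but do not remove it, because the questions still concern a program these facilitators delivered.

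Fourth, the application says the semi-structured questions are unfinished and will go to the IRB, and the consent form, which may describe the session, is not in the text available for this review. The absence of a separation rule therefore holds for the text available. It also means the point can be settled at little cost.

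**Conclusion.** The point holds as an unresolved inconsistency with a plausible consequence. Appendix 3 as worded allows facilitators and caregivers in one focus group. The procedures describe a participant group, and no section available for review separates the two, keeps a session facilitator from moderating, or separates the sources in analysis.

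If the session is run as Appendix 3 reads, muted criticism is a credible risk in one of several acceptability sources and in part of the feedback used between groups. The size is unknown. A reader might go further and conclude that acceptability will be overstated in every focus group. Overstatement is the likely direction if facilitators attend, but the documents neither show it nor establish that they would attend every group.

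The conclusion rests on two assumptions: that the plain reading of item 2 could be put into practice, and that the removed consent form does not already separate the two groups. This is a low-cost improvement to the plan, not a flaw that invalidates the pilot.

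**What to change.** Bring Appendix 3, item 2, and Methods and Procedures, question 4, into agreement:

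- Hold caregiver focus groups without program facilitators.
- Have each led by a research team member who did not deliver that group's sessions.
- Collect facilitator views in a separate short session.
- In question 6, state that caregiver and facilitator material is coded and reported separately.

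The cost is one extra short session with the facilitators. No new participants or measures are needed, the research-team moderator is already planned, and the change can go in with the focus-group materials that the application says are still to be submitted to the IRB.

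If any joint session has already been held, report who attended it and state this as a limitation of the focus-group findings.
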